## BACKGROUND INFORMATION

Hypersensitivity pneumonitis (HP) is an immunologically mediated form of interstitial lung disease (ILD), in response to inhalation exposure to a large variety of antigens, of varying intensity, clinical presentation and natural history.

In the USA, the one-year prevalence rates for HP range from 1.39 to 2.06 cases per 100,000 persons and incidence rates range from 0.82 to 1.74 cases per 100,000. The prevalence and incidence of HP increased with age. Among adults aged 65 and over, prevalence rates range from 3.63-6.57 cases per 100,000 persons and incidence rates range from 2.41-5.18 cases per 100,000.

A subgroup of patients with HP develops fibrotic HP (FHP), characterized clinically by ventilatory restriction and the presence of chest imaging or pathologic evidence of lung fibrosis. FHP is an irreversible and often progressive disease that distorts the lung architecture and ultimately results in hypoxemia and respiratory failure. The presence of lung fibrosis on HRCT scans and/or in surgical lung biopsy specimens is the strongest predictor of death. When fibrosis is present, the median survival time may be similar to those with IPF (4.9 years; 95% CI, 2.9-7.5). Indeed, FHP shares similarities with the most devastating of the ILD, namely IPF. FHP can lead to end-stage pulmonary fibrosis with excessive collagen and extracellular matrix deposition. Also, IPF and FHP are known to have overlapping clinical manifestations, contributing risk factors (e.g., cigarette smoking, aging) and comorbidities (e.g., pulmonary hypertension), histopathologic features and prognosis. Patients with FHP most commonly present with the insidious onset of progressive exertional dyspnea and a non-productive chronic cough. While patients may encounter periods of clinical, radiologic and functional stability, or slow and gradual progression over many years, others may experience an accelerated decline over months. At any time during the disease course patients may experience acute respiratory exacerbations. These events are unpredictable and sometimes fatal.

Management of FHP is aimed at antigen identification and avoidance. Antigen avoidance can favorably influence FHP survival. Nevertheless, we have shown that even after adjusting for the presence of fibrosis, patient age, pulmonary function and smoking history, survival was shorter for patients with an unidentified inciting antigen (IA) exposure than those with an identified IA exposure (median, 4.88 years vs. 8.75 years), suggesting that pre-existing genetic susceptibility increases the risk of disease progression regardless of the presence or absence of IA. Immunomodulatory therapy, such as corticosteroids and azathioprine is commonly initiated when clinically significant disease progression is recognized. However, it is increasingly clear that traditional immunomodulatory therapy (e.g., corticosteroids) does not target key active profibrotic pathways in susceptible FHP patients and that a subset of patients develops a progressive disease phenotype. Results from previous clinical trials suggest that pirfenidone is well tolerated and may slow the decline in or lead to stabilization of pulmonary function in patients with IPF. IPF is a fibrotic lung disease that shares overlapping pathways with FHP. Given the efficacy and safety in previous IPF trials,

treatment with pirfenidone may be of value in FHP and should be tested for its clinical efficacy in a well-characterized disease. In an open-label study of 10 patients with pulmonary fibrosis, pirfenidone was well tolerated and no significant adverse effects occurred during one-year treatment when in combination with corticosteroids or azathioprine.

The main goal of the current study is to evaluate the clinical effect of pirfenidone on disease progression and assess the safety and tolerability, in particular when in combination with immunomodulatory drugs, among subjects with different severities of FHP.

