### *Multidisciplinary Consensus Diagnosis of FHP\**

- a. Diagnosis of FHP (**figure**), defined from the first instance in which a patient was informed of having FHP for at least 3 to 6 months.
- b. Age 18 through 80 years at randomization.
- c. Diagnosis of typical or compatible FHP by HRCT according to pre-specified criteria  
(Note: HRCT scan performed within 4 months of the start of screening may be used if it meets image acquisition guidelines):
  - a. Typical FHP: Evidence of lung fibrosis (reticular abnormality and/or, traction bronchiectasis and/or, architectural distortion, and/or honeycombing) with either of the following:
    - i. Profuse poorly defined centrilobular nodules of ground-glass opacity affecting all lung zones.
    - ii. Inspiratory mosaic attenuation with three-density sign.  
AND
    - iii. Lack of features suggesting an alternative diagnosis.

These patients are required to have an identifiable antigen exposure, or an indeterminate or unidentifiable antigen exposure and BAL lymphocytosis ( $\geq 20\%$ ) or transbronchial biopsies demonstrating non-necrotizing granuloma(s) or lymphocytosis, or surgical lung histology consistent with HP.

- b. Compatible FHP: Evidence of lung fibrosis (as above) with any of the following:
  - i. Patchy or diffuse ground-glass opacity.
  - ii. Patchy, non-profuse centrilobular nodules of ground-glass attenuation
  - iii. Mosaic attenuation and lobular air-trapping that do not meet criteria for typical fibrotic HP.  
AND
  - iv. Lack of features suggesting an alternative diagnosis.

These patients are required to have an identifiable or indeterminate antigen exposure and BAL lymphocytosis ( $\geq 20\%$ ) or transbronchial biopsies demonstrating non-necrotizing granuloma(s) or lymphocytosis, or surgical lung histology consistent with HP. Otherwise, surgical lung histology consistent with HP.

c. Indeterminate FHP: CT signs of fibrosis without other features suggestive of HP and lack of features suggesting an alternative diagnosis. These patients are required to have a known antigen exposure and BAL lymphocytosis ( $\geq 20\%$ ) or transbronchial biopsies demonstrating non-necrotizing granuloma(s) or lymphocytosis, or surgical lung histology consistent with HP.

[figure not shown]
*FHP Disease Severity and Progression*

4. FVC  $\geq 40\%$ , DLCO  $\geq 30\%$  based either on historical pulmonary function tests obtained within the 60 days prior to Day 1

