5. In the investigator's opinion, evidence of disease progression: worsening respiratory symptoms and an increased in extent of fibrosis on HRCT or relative decline in the FVC% of at least 5% over 24 months.
6. Able to walk  $\geq 100$  m during the 6-minute walk test (6MWT) at Screening.

*Informed Consent and Protocol Adherence*

7. Able to understand and sign a written informed consent form.
8. Able to understand the importance of adherence to study treatment and the study protocol and willing to follow all study requirements, including the concomitant medication restrictions, throughout the study

*Eligibility criteria summary (multidisciplinary discussion):*

**\*HP Diagnosis - Multidisciplinary Adjudication Committee:** the multidisciplinary discussion will be performed at the weekly NJH ILD conference attended by seven pulmonologists, one radiologist, and one pathologist. During the conference, the

exposure history (identified, indeterminate [evidence is suggestive of an association], or unidentified inciting antigen exposure), clinical details and radiologic and pathologic images will be presented. The expert chest radiologist and the expert pathologist will interpret the radiological and histological features. The final multidisciplinary diagnosis adjudication will be documented on a case report form. Differences of opinion regarding diagnostic eligibility will be resolved through consensus adjudication.

Patients with a provisional low-confidence diagnosis or HP unlikely may require surgical lung biopsy HP histology data for inclusion as determined by the adjudication committee.

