## **STATISTICAL METHODS**

### **Randomization and Treatment Assignment**

In this double-blind study, subjects will be randomized to receive either pirfenidone 2403 mg/d or placebo in a 2:1 ratio.

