## **Efficacy Analyses**

### **Primary Efficacy Outcome Variable and Analysis**

The primary efficacy analysis will estimate the mean rank change in %FVC from Baseline to Week 52. Data will be analyzed using a rank linear regression model with the rank change in %FVC from Baseline to Week 52 as the outcome variable and rank Baseline %FVC and HP therapy (placebo or pirfenidone) and concomitant immunosuppressive therapy as covariates. The treatment effect will be tested using the Wald test.

The primary efficacy analysis will be tested at an alpha level of 0.05. Missing data due to reasons other than death will be replaced with imputed values using the MICE method (multiple imputation via chained equations). Missing data due to lung transplant will be imputed using the MICE method even if the subject dies after lung transplant.

Subjects with missing assessments due to death will be ranked worse than those who remain alive. Subjects who die will be ranked according to the time until death, with the shortest time until death as the worst rank.

Supportive analyses of the primary efficacy outcome will include the following:

1. Landmark analyses of mean change in %FVC from Baseline to Weeks 13, 26, 39 and 52.
2. Mean rank change in %FVC compared to Baseline across all study time points using a rank linear mixed effects model for repeated measures.

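### Antigen status, which the protocol itself reports as prognostic, is used in neither the described randomization nor any efficacy model, which gives up precision and protection against an unlucky allocation

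*Combined protocol and SAP*

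**What the plan says.** **The prognostic evidence.** Background Information reports the investigators' own survival data: "survival was shorter for patients with an unidentified inciting antigen (IA) exposure than those with an identified IA exposure". The comparison is "with an identified IA exposure (median, 4.88 years vs. 8.75 years", and the difference held "even after adjusting for the presence of fibrosis, patient age, pulmonary function and smoking history". The same sentence gives the protocol's interpretation: "suggesting that pre-existing genetic susceptibility increases the risk of disease progression regardless of the presence or absence of IA".

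**Who enters.** The inclusion criteria admit patients across the exposure categories, with supporting lavage or biopsy evidence where the antigen is uncertain. For typical FHP on HRCT: "These patients are required to have an identifiable antigen exposure, or an indeterminate or unidentifiable antigen exposure and BAL lymphocytosis".

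**When status is known.** The eligibility criteria summary says that the multidisciplinary conference is shown the "exposure history (identified, indeterminate [evidence is suggestive of an association], or unidentified inciting antigen exposure". The final diagnosis goes on a case report form. The text does not say that the exposure category is recorded there as its own field.

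**Randomization.** Statistical Methods says only that "subjects will be randomized to receive either pirfenidone 2403 mg/d or placebo in a 2:1 ratio". Study Design, Randomization and Blinding, and the Day 1 randomization text name no stratification factor, blocking or minimization.

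**Models.** The primary rank regression uses "rank Baseline %FVC and HP therapy (placebo or pirfenidone) and concomitant immunosuppressive therapy as covariates". Under Key Secondary Efficacy Outcome Variables and Analyses, no model (PFS, mortality, FVC slope, DLCO, hospitalization, CT progression) names antigen status. No subgroup or sensitivity analysis by antigen status is planned.

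**The concern.** The protocol describes antigen status as carrying prognostic information beyond lung function, so the baseline %FVC term cannot be relied on to absorb it. Fibrosis, which the protocol calls the strongest predictor of death, is required for entry, so its presence cannot separate these patients. Antigen status can.

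With about 14 placebo patients, a sizeable chance difference in antigen mix between the arms is quite possible. If antigen status is related to 52-week FVC change, two things are at stake. Residual variance that a baseline term could remove stays in the error. And if the realised allocation is unbalanced, the reported estimate is shifted, with no prespecified analysis to separate that shift from the drug effect. Adding the term after seeing the imbalance would be open to challenge.

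**Working it through.** **Inputs from Sample Size and Power Considerations:** 13 placebo and 25 pirfenidone patients, difference 2 points, SD 2 points, two-sided alpha 0.05, 42 randomized 2:1 (28:14).

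**Inputs not in the documents, so assumed:** share with unidentified antigen 30-70%; effect of antigen status on 52-week %FVC change 0, 1 or 2 points, with total SD held at 2.

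1. **The plan's own power figure.** SE of the arm difference = 2 × √(1/13 + 1/25) = 0.68. The normal approximation gives 83.3% power. The two-sample t-test that the plan names gives 81.2%. The plan states at least 85%, so there is no spare power to give away.

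2. **Chance imbalance.** Under unstratified 28:14 allocation, the number of unidentified-antigen patients on placebo is hypergeometric (42 patients, K unidentified, 14 drawn). With x on placebo, the difference in shares is (K − x)/28 − x/14.

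| Share (K of 42) | SD of difference | P(≥20 points) | P(≥30 points) |
|---|---|---|---|
| 30% or 70% (13 or 29) | 15 points | 16% | 3% |
| 40% or 60% (17 or 25) | 16 points | 18% | 4.5% |
| 50% (21) | 17 points | 33% | 10% |

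   These are two-sided; roughly half of each probability favours pirfenidone. The 50% row stands out partly because the attainable differences are discrete: there, 21.4 points is attainable and counts as at least 20.

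3. **Shift in the estimate** = imbalance × antigen effect. For 20 points: 0.20 × 1 = 0.2 and 0.20 × 2 = 0.4. For 30 points: 0.30 × 1 = 0.3 and 0.30 × 2 = 0.6. The target is 2 points, so the shift is 10-30% of it. This is on the mean scale; the primary model works on ranks, so it is a guide only.

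4. **Is the shift outside the planned error?** At 50% share, the SD of the shift over allocations is 0.166 × 1 = 0.17 or 0.166 × 2 = 0.33 points, against an SE of 0.68. That variation is already part of the SE.

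5. **Rank model with and without the antigen term.** Simulation at 25/13, 50% share, 40,000 trials per setting. It omits deaths, imputation and the immunosuppression covariate.

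| Assumed antigen effect | Type I error without / with term | Power for 2-point drug effect without / with term |
|---|---|---|
| 0 points | 4.9% / 4.9% | 78% / 77% |
| 1 point | 5.0% / 5.0% | 78% / 79% |
| 2 points | 5.1% / 4.9% | 77% / 87% |

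   Repeat runs agree to within about 1 point of power.

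6. **Given an unlucky draw.** An imbalance of at least 20 points favouring pirfenidone occurs in 8-9% of simulated trials. Among those, type I error without the term is 6.6% (1-point effect) or 12.9% (2-point effect). With the term it is 5.3% or 4.9%.

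**The case against.** The strongest reply has four parts.

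- **The evidence is about survival over years, not %FVC over 52 weeks.** This stands. No figure in the documents links antigen status to the primary endpoint. The source analysis adjusted for the presence of fibrosis, which implies a cohort with and without it. This trial takes only fibrotic patients with evidence of progression and excludes sustained improvers, which may narrow any antigen difference. Survival is not wholly remote, because the primary analysis ranks deaths worst, but that route is small. If survival were exponential (an assumption), the two medians imply one-year mortality of about 13% and 8%. A 32-point imbalance would then move the expected placebo deaths by about 0.25 of a death (0.32 × 0.056 × 14).
- **The association need not be causal.** This stands. A reader might infer that identifying the antigen itself alters the course of disease. The protocol attributes the difference to genetic susceptibility. Covariate adjustment needs only a prognostic marker, however, so this does not remove the point.
- **Randomization already keeps the test valid.** This also stands. A reader might infer that the plan is biased, or that an imbalance could readily pass for a drug effect. The documents do not support that. The overall error rate is about 5% without the term, the inflation in step 6 is conditional on an unlucky draw, and a shift of 0.2-0.6 points is below one SE.
- **Two covariates are already specified, and a third is a matter of taste with about 14 placebo patients.** This stands only in part. The plan accepts covariate adjustment in principle, and the cost of one more two-level term is about 1 point of power.

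Two limits remain. The absence of stratification is read from silence. And the published contrast is identified against unidentified, so nothing in the documents places the indeterminate group.

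**Conclusion.** The omission is real and worth correcting, as a matter of efficiency and robustness. A factor that the protocol presents as prognostic beyond lung function is reviewed for eligibility and then not used. The primary test remains valid without it.

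The size rests entirely on assumed values for prevalence and for the effect on FVC. Over 30-70% prevalence, imbalances of at least 20 points arise in 16-33% of allocations and of at least 30 points in 3-10%. With a 1-2 point effect, imbalances of that size move the estimate by about 0.2-0.6 points. The gain in power from adjusting is material only towards the upper assumption: about 1 point at a 1-point effect and 9-10 points at 2. Against that stands a loss of about 1 point if antigen status is unrelated to FVC change. That asymmetry, in a trial whose named t-test gives 81.2% power, is the reason to act.

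**What to change.** Before unblinding:

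- Record the conference-adjudicated antigen category as its own field on the adjudication case report form, before Day 1.
- Prespecify it as a two-level covariate (identified or not identified), and state in advance on which side the indeterminate category falls.
- Add it to the primary rank regression, the DLCO rank regression and the FVC-slope model. In the slope model it should enter with its interaction with time, since a main effect alone adjusts level and not rate of decline.
- Report antigen status by arm in the baseline table.

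No change to randomization is needed. If antigen status is made a stratification factor, it must also be in the model. In the same simulation, stratifying without adjusting made the test conservative, with type I error of 4.4% at a 1-point effect and 2.6% at a 2-point effect.

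The cost is a few sentences in the analysis section, one field on a form that is already completed, one residual degree of freedom in the primary model, and about 1 point of power if the factor proves irrelevant.

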### **Description**

Pirfenidone is a small non-peptide molecule of low molecular weight (185.2 daltons). Its chemical name is 5-methyl-1-phenyl-2-(1H)-pyridone, and its empirical formula is C12H11NO. It is an antifibrotic agent with anti-inflammatory properties. Pirfenidone was approved by European and US regulatory agencies in 2011 and 2014, respectively, for the treatment of IPF.

### **Potential Benefits and Risks to Human Subjects**

The safety of pirfenidone has been characterized in 15 studies involving 1345 subjects and patients; 770 patients have received pirfenidone at a dose of 2403 mg/d or greater. Analyses of this data suggest that the side effects of pirfenidone are readily monitored, typically reversible, and related to tolerability rather than morbidity.

In the LOTUSS study (An Open Label, Randomized, Phase 2 Study of the Safety and Tolerability of Pirfenidone when Administered to Patients with Systemic Sclerosis-Related Interstitial Lung Disease) designed to assess the safety and tolerability of pirfenidone in patients with SSc-ILD at the same therapeutic dose used in IPF, and using 2 dose-titration schedules (4-weeks vs. 2-weeks), with or without stable background systemic sclerosis-ILD therapy; mycophenolate (commonly utilized in HP) was received by 63% of patients in addition to pirfenidone, with similar tolerability to pirfenidone alone. Further, patients who took pirfenidone and mycophenolate, compared with pirfenidone alone, appeared to experience fewer treatment emergent adverse events and discontinuations. A longer dose titration, 4-weeks as opposed to 2-weeks, had more favorable effect on tolerability. Escalation of dose over the first 4 weeks, dosing with food, use of protection against sun exposure, prompt symptomatic management of intolerance, and monitoring of liver function tests during dosing are recommended to maximize tolerability.

### **Study Rationale**

FHP is a life-threatening and severely debilitating disease. Currently, there is lack of efficacious therapeutic options. Results from four controlled trials, suggest that pirfenidone treatment is safe and well tolerated and results in clinically meaningful benefits in a variety of domains, exercise tolerance (change in 6MWT distance), and progression-free survival time in patients with IPF. Given the primacy of loss of lung volumes over time in

patients with FHP, this protocol is intended to confirm that pirfenidone 2403 mg/d reduces decline in %FVC over 52 weeks and that it is safe and tolerable, as observed in the previous IPF studies.

## INVESTIGATIONAL PLAN

### Objective

- To evaluate the treatment effect of pirfenidone 2403 mg/d compared with placebo on the mean change of percent predicted forced vital capacity (%FVC) in subjects with fibrotic hypersensitivity pneumonitis (FHP).
- To assess the safety and tolerability of pirfenidone at 2403 mg/d when administered to subjects with FHP.

### Study design

This is a single-center, randomized, double-blind, placebo-controlled, efficacy and safety study of pirfenidone in subjects with FHP. Approximately 42 subjects will be randomized in a 2:1 ratio to receive pirfenidone 2403 mg/d or placebo for 52 weeks. The primary efficacy endpoint is the mean change in %FVC from Baseline to Week 52, to be analyzed using a rank linear model. Subjects will receive blinded study treatment from the time of randomization until the Week 52 Visit.

Eligible subjects, males and females, aged 18–80 years (inclusive) must have a confident or high-confidence diagnosis of FHP according to pre-specified criteria without evidence of an alternative diagnosis that may contribute to their interstitial lung disease. Subjects will be required to have a FVC  $\geq$ 40% and DLCO  $\geq$ 30% at screening.

Subjects will enter the Screening Period, which may last up to 30 days. In addition of brief periods of corticosteroid use for acute FHP exacerbation, subjects will be allowed to receive any other therapy for the treatment of FHP as per pre-specified criteria.

The dose of study treatment will be titrated over 4 weeks (2 weeks at 1 capsule TID; 2 weeks at 2 capsules TID; and 48 weeks at 3 capsules TID (2403 mg/d). Pirfenidone dose modifications or interruption will be allowed for safety or tolerability reasons at any time during the study.

Subjects will have a telephone assessment at Week 1 and 3, and an in-clinic assessment at day 1, weeks 5, 13, 26, 39, and 52. Subjects will be asked to complete an adverse event (AE) and dosing compliance diary between all visits. If subjects discontinue study treatment early for any reason, they will be asked to continue with all scheduled study procedures through Week 52.

A Safety officer will review all deaths and monitor subject safety during the study.

